APPENDIX 3. PATIENT REPORTED OUTCOMES

Participant ID:	
-----------------	--

Participant Initials: Date: 1

FLU-PRO Plus®

People experience viral respiratory tract infections in different ways. We would like to know about the symptoms you have been experiencing during the past 24 hours. For each symptom, please mark one box
under the response that best matches your experience. if you did not have that symptom in the past 24 hours. Mark

What time is it? _____AM / PM (please circle)

Please rate the extent to which you had each symptom during the past 24 hours.

Runny or dripping nose		
Congested or stuffy nose		
Sinus pressure		
Scratchy or itchy throat		
Sore or painful throat		
Difficulty swallowing		
Teary or watery eyes		
Sore or painful eyes		
Eyes sensitive to light		
Trouble breathing		
Chest congestion		
Chest tightness		
Dry or hacking cough		
Wet or loose cough		
Felt nauseous (feeling like you wanted to throw-up)	1	
Stomach ache		
Felt dizzy		
Head congestion		
Headache		
© 2014 Leidos Biomedical	August 20, 2015 FLU-PRO Version 2.0	Page 1 of 2

Page 1 of 2

CTAP101 | CTAP101-CL-2014 | CTAP101-CL-2014 Protocol VV-TMF-183735 | Version 8.0 dated 16 Nov 2021

Protocol CTAP101-CL-2014 CTAP101 (calcifediol) Extended-release Capsules

Participant ID:

Participant Initials: ____Date: / /

Please rate the extent to which you had each symptom during the past 24 hours.

Lack of appetite
Sleeping more than usual
Body aches or pains
Weak or tired
Chills or shivering
Felt cold
Felt hot
Sweating

In the past 24 hours, how often have you had any of the following symptoms?

How	w many times did you nit?
How	w many times did you have rrhea?

In the past 24 hours, did you have any of the following symptoms?

Loss of smell	
Loss of taste	

© 2014 Leidos	August 20, 2015 FLU-PRO Version 2.0		
Biomedical		Page 2 of 2	
Research, Inc.	Research Tool in Development:		

OPKO Pharmaceutcials, LLC Page 81 of 82

FLU-PRO^c GLOBAL ADDITIONAL DAILY DIARY ITEMS

Items to be asked in daily diary for the length of the study along with the FLU-PRO symptom items.

1. Overall, how severe were your infection symptoms today? (Please select one response only)

2. Overall, how were your infection symptoms today compared to yesterday? (Please select one response only)

3. How much did your infection symptoms interfere with your usual activities today? (Please select one response only)

4. Have you returned to your usual activities today?

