The severity, duration and clinical course of COVID-19 illness will be compared between treatment groups by analyzing changes in quality-of-life assessments recorded on the FLU-PRO Plus[©] questionnaire. Five of the six items from the questionnaire to be analyzed are: "Overall, how severe were your infection symptoms today?", "Overall, how were your infection symptoms today compared to yesterday?", "How much did your infection symptoms interfere with your usual activities today?", "Have you returned to your usual activities today?", "In general, how would you rate your physical health today?", and "Have you returned to your usual health today?" The scores for: symptom severity range from 0 (no infection symptoms today) to 4 (very severe); symptoms today range from 1 (much better) to 7 (much worse); symptom interference range from 1 (not at all) to 5 (very much). The first of two consecutive scores of ≤ 1 spanning at least three days and no more than five days will be considered the day of resolution, provided that no intervening scores of >1 are recorded. The scores for return to usual activities or health are either "yes" or "no", and the first occurrence of "yes" will be deemed to be day of resolution provided that a second "yes" is recorded no more than 5 days later without an intervening "no". The remaining sixth item to be analyzed is: "physical health range from 1 (poor) to 5 (excellent). The first of two consecutive scores of >4 spanning at least three days and no more than five days will be considered the day of resolution, provided that no intervening scores of <4 are recorded. Each item will be compared between treatment groups using a Cox proportional hazards model with covariates (aggregate FLU-PRO Plus[©] score for the selected five COVID-19 symptoms at baseline, serum total 25D at baseline, and body weight).

The clinical course of COVID-19 will be examined by subgroups defined by serum total 25D levels <50 ng/mL, 50 to 100 ng/mL and >100 ng/mL at Days 7, 14, 21 and 28.

 	

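### Three event and entry rules for the quality-of-life items (secondary endpoint 8) do not fit the scales: a day-to-day change item is timed as resolution, a physical-health score of 4 is left undefined, and the baseline filter runs the wrong way for physical health

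*SAP*

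**What the plan says.** Secondary endpoint 8 is the severity and duration of illness shown by the quality-of-life items of the daily questionnaire (SAP 5.3; Protocol 3.4.2). The event rules are in SAP 6.10.2, with the same text in Protocol 9.10.2 and the protocol synopsis.

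- **Severity, change and interference items.** One rule serves all three: the day of resolution is the first of two scores of 1 or less spanning three to five days, "provided that no intervening scores of >1 are recorded". The scales differ. Severity runs from 0 (none) to 4, and interference from 1 (not at all) to 5. For the change item, "symptoms today range from 1 (much better) to 7 (much worse". Protocol Appendix 3 words that item as "Overall, how were your infection symptoms today compared to yesterday? (Please select one response only".
- **Physical health.** The scale is given as "physical health range from 1 (poor) to 5 (excellent". The event is "The first of two consecutive scores of >4 spanning at least three days and no more than five days", "provided that no intervening scores of <4 are recorded".
- **Item list.** The paragraph opens with "Five of the six items from the questionnaire to be analyzed are" but then lists six items. Physical health is among them, and it appears again as the remaining sixth.
- **Analysis.** "Each item will be compared between treatment groups using a Cox proportional hazards model with covariates".
- **Analysis set.** SAP 4.3 and Protocol 9.5 exclude, for each quality-of-life response, any subject whose baseline score on that response is not above 1. No exception is made for a scale on which higher is better, or for the yes/no items.

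**The concern.** A time-to-resolution analysis needs an event that marks recovery, a rule that classifies every possible score, and an analysis set of subjects who have not yet reached the event. Each of these fails for at least one item.

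On the change item, a score of 1 describes a fast rate of improvement, not a good state. The hazard ratio would therefore compare how often subjects have a spell of rapid improvement. The planned tables would nevertheless report it under duration of illness (Tables 14.2.2.11 and 14.2.2.12). On physical health, the event and its date depend on how the programmer treats a 4. The baseline filter removes from that item the subjects with most room to recover.

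The severity and interference rules are not in question. Neither is the three-day minimum for the yes/no items, which SAP 6.2 sets by reference to Section 5.2.

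**Working it through.** The plan gives no figure to reproduce here, so the rules were applied to the scales and to example score paths.

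**Event algorithm.** The event is the first day i with a qualifying score on day i and on a later day j, where the inclusive span j − i + 1 is 3 to 5 and no breaking score lies between.

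**1. Change item** (qualifies at 1 or less; above 1 breaks). The labels between 1 and 7 are not in the text. The check needs only that a subject who reports no change does not score 1, because 1 is much better.

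| Scores | Event |
|---|---|
| 1, 1 on Days 5–6, then no change through Day 42 | none (span 2 days) |
| 1, 1, 1 on Days 5–7 | Day 5, whatever the severity score |
| 3, 3, 3, 2, 2, 3, 4, 4, 4, 4 (gradual improvement) | none |

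**2. Physical health.** Classifying each score under the written rules:

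| Score | Qualifies (>4) | Breaks (<4) | Baseline filter (>1) |
|---|---|---|---|
| 1 (poor) | no | yes | excluded |
| 2 | no | yes | kept |
| 3 | no | yes | kept |
| 4 | no | no | kept |
| 5 (excellent) | yes | no | kept |

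For the other scored items the limits are exact complements (1 or less against above 1), so no score is left over. The next table sets the written rule, with a 4 allowed between qualifying scores, against the two complementary versions. Scores before the stated days are 3 or lower.

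| Scores | As written | ≥4, broken by <4 | >4, broken by ≤4 |
|---|---|---|---|
| 4 daily, Days 6–42 | none | Day 6 | none |
| 5, 4, 5 on Days 8–10, then 3 | Day 8 | Day 8 | none |
| 5, 4, 4, 4, 5 on Days 8–12, then 3 | Day 8 | Day 8 | none |
| 4, 4, 5, 5, 5 on Days 6–10 | Day 8 | Day 6 | Day 8 |

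In the first row the subject either has an event on Day 6 or is event-free through nominal Day 42, which is 42 − 6 = 36 further days of follow-up.

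There are 5^5 = 3,125 complete five-day sequences. Across all of them:

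- the written rule differs in event day or status from the >4/≤4 version in 84 (84/3,125 = 2.7%);
- it differs from the ≥4/<4 version in 312 (312/3,125 = 10.0%);
- the two complementary versions differ from each other in 385 (385/3,125 = 12.3%).

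These counts weight every sequence equally and are not expected patient frequencies.

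**3. Baseline filter.** The last column of the classification table shows the reversal: the worst level is removed, and a subject already at 5 stays and can have the event at once. Few subjects should start at 5, because inclusion criterion 4 requires symptoms inconsistent with usual health. For the two yes/no items a numeric cut at 1 has no meaning.

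**4. Is it corrected elsewhere?** SAP 6.2 sends the quality-of-life items to Section 5.2, but that section defines resolution only for the aggregate score of 5 or less. It settles none of the three points.

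**The case against.** Several counter-arguments have weight.

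- **The all-4 case shows the choice of threshold, not the gap.** This is correct: the written rule agrees there with the >4/≤4 version. The gap by itself matters only for patterns such as 5, 4, 5, which account for the 84 sequences. Day 42 is also nominal, since Visit 6 has a window of ±4 days.
- **Two consecutive scores above 4 may already rule out a 4 in between.** On that reading 5, 4, 5 gives no event. But in a complete daily diary two strictly adjacent scores span two days, not three, so the rule must allow scores between the qualifying pair. The limit for those scores is below 4, which is silent on 4. The text is at best ambiguous.
- **The sign may be a slip for ≥4.** This is possible, because inequality signs vary elsewhere in the documents. The same sign appears in all three places, so the sponsor has to say which was meant. The other two points do not depend on it.
- **The reach is small.** Endpoint 8 lies outside the alpha hierarchy and is not among the seven secondary endpoints listed for nominal p-values. Four of the six event rules are unchallenged. No figure shows how many subjects start at poor. This limits the importance but does not make the rules right.
- **By-visit quality-of-life tables are already planned** (14.2.2.9 and 14.2.2.10), so a new model is not essential. This stands, and the fix below allows for it.

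The miscount of five and six items is editorial, since physical health has its own rule.

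**Conclusion.** The concern holds on all three points and should be fixed. Followed exactly, the plan would report a hazard ratio for spells of rapid improvement as though it measured duration of illness. It would leave the physical-health event to a programming choice at score 4. It would also analyse physical health in a set that leaves out the worst baseline level.

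The size in this trial is unknown, because the documents give no score distribution; the worked paths and sequence counts show what the rules do, not how often. The conclusion on the change item assumes only that a subject reporting no change scores above 1. The 5, 4, 5 results assume that a 4 may sit between qualifying scores. Scope is the item-level analysis of secondary endpoint 8. The primary endpoints and the one-sided 0.025 are untouched, and no bias between arms is shown.

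**What to change.** Make these changes before unblinding.

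1. **Change item.** Take it out of the time-to-resolution analyses. Summarise or compare it between arms as an ordinal daily score, for example with a repeated-measures cumulative-logit model using the same three covariates, in its own table. The minimum is to drop it from the Cox set and rely on the by-visit tables.
2. **Physical health.** State one complementary rule: either 4 or above with no intervening score below 4, or above 4 with no intervening score of 4 or below. The sponsor confirms which was intended. Remove the item from the list introduced as five of the six.
3. **Baseline entry.** For physical health, require a baseline below the chosen threshold. For the yes/no items, require a baseline answer of no. Keep above 1 for severity and interference.

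The edits belong in SAP 4.3 and 6.10.2. The SAP states that it supersedes the protocol, so these suffice; matching changes to Protocol 9.5, 9.10.2 and the synopsis are for consistency. The cost is low but goes beyond wording: one pre-specified Cox comparison is dropped or replaced, a table may be added, and the analysis sets for physical health and the yes/no items change. No new data are needed.

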7 REVISION HISTORY

Version	Date (dd-mmm- yyyy)	Summary of Changes
1.0	04-Aug-2021	Original.

8 TABLES, LISTINGS AND FIGURES

8.1 List of Tables

The Tables to be generated include, but not limited to the following:

CONDUCT OF STUDY

14.1.1	Disposition of Subjects: All Enrolled Subjects
14.1.1.1	Major Protocol Deviations: Full Analysis Population
14.1.2.1	Demographics and Baseline Characteristics: Intent-to-Treat Population
14.1.2.2	Demographics and Baseline Characteristics: Full Analysis Population
14.1.2.3	Demographics and Baseline Characteristics: Per Protocol Population
14.1.2.4	Demographics and Baseline Characteristics: Safety Population
14.1.3	Prior and Concomitant Medications by ATC Level 2 and Preferred Term: Safety
	Population

PRIMARY EFFICACY ENDPOINTS

[figure not shown]
14.2.1.1	Attainment of Serum 25D Levels >=50 ng/mL by Visit: Full Analysis Population
14.2.1.2	Attainment of Serum 25D Levels >=50 ng/mL by Visit: Per Protocol Population
14.2.1.3	Attainment of Serum 25D Levels >=50 ng/mL by Visit and by Subgroups: Full
	Analysis Population
14.2.1.4	Attainment of Serum 25D Levels >=50 ng/mL by Visit and by Subgroups: Per
	Protocol Population
14.2.1.5	Time to Resolution of COVID-19 Symptoms Based on FLU-PRO Plus COVID-
	19 Five Symptom Aggregate Score: Full Analysis Population
14.2.1.6	Time to Resolution of COVID-19 Symptoms Based on FLU-PRO Plus COVID-
	19 Five Symptom Aggregate Score: Per Protocol Population
14.2.1.7	Time to Resolution of COVID-19 Symptoms Based on FLU-PRO Plus COVID-
	19 Five Symptom Aggregate Score - Cox Proportional Hazards Model Summary
	of Effects: Full Analysis Population
14.2.1.8	Time to Resolution of COVID-19 Symptoms Based on FLU-PRO Plus COVID-
	19 Five Symptom Aggregate Score - Cox Proportional Hazards Model Summary
	of Effects: Per Protocol Population
14.2.1.9	Tipping Point Analysis for Time to Resolution of COVID-19 Symptoms Based
	on FLU-PRO Plus COVID-19 Five Symptom Aggregate Score: Full Analysis
	Population
14.2.1.10	Tipping Point Analysis for Time to Resolution of COVID-19 Symptoms Based
	on FLU-PRO Plus COVID-19 Five Symptom Aggregate Score: Per Protocol
	Population
14.2.1.11	Time to Resolution of COVID-19 Symptoms Based on FLU-PRO Plus COVID-
	19 Five Symptom Aggregate Score by Subgroups: Full Analysis Population
14.2.1.12	Time to Resolution of COVID-19 Symptoms Based on FLU-PRO Plus COVID-
	19 Five Symptom Aggregate Score by Subgroups: Per Protocol Population

14.2.1.13 Resolution of COVID-19 Symptoms Based on FLU-PRO Plus COVID-19 Five Symptom Aggregate Score Based on Serum 25D Level at Day 7: Full Analysis Population 14.2.1.14 Resolution of COVID-19 Symptoms Based on FLU-PRO Plus COVID-19 Five Symptom Aggregate Score Based on Serum 25D Level at Day 7: Per Protocol Population 14.2.1.15 Resolution of COVID-19 Symptoms Based on FLU-PRO Plus COVID-19 Five Symptom Aggregate Score Based on Serum 25D Level at Day 14: Full Analysis Population 14.2.1.16 Resolution of COVID-19 Symptoms Based on FLU-PRO Plus COVID-19 Five Symptom Aggregate Score Based on Serum 25D Level at Day 14: Per Protocol Population Resolution of COVID-19 Symptoms Based on FLU-PRO Plus Aggregate Score 14.2.1.17 Symptoms Based on Serum 25D Level at Day 21: Full Analysis Population Resolution of COVID-19 Symptoms Based on FLU-PRO Plus Aggregate Score 14.2.1.18 Symptoms Based on Serum 25D Level at Day 21: Per Protocol Population Resolution of COVID-19 Symptoms Based on FLU-PRO Plus COVID-19 Five 14.2.1.19 Symptom Aggregate Score Based on Serum 25D Level at Day 28/ET: Per **Protocol Population** Resolution of COVID-19 Symptoms Based on FLU-PRO Plus COVID-19 Five 14.2.1.20 Symptom Aggregate Score Based on Serum 25D Level at Day 28/ET: Per **Protocol Population** 14.2.1.21 COVID-19 Symptom Relapse After Initial Resolution Based on FLU-PRO Plus COVID-19 Five Symptom Aggregate Score: Full Analysis Population COVID-19 Symptom Relapse After Initial Resolution Based on FLU-PRO Plus 14.2.1.22 COVID-19 Five Symptom Aggregate Score: Per Protocol Population Sensitivity Analysis for Resolution Based on Number of Consecutive Days with 14.2.1.23 FLU-PRO Plus COVID-19 Aggregate Score <=5: Full Analysis Population 14.2.1.24 Sensitivity Analysis for Resolution Based on Number of Consecutive Days with FLU-PRO Plus COVID-19 Aggregate Score <=5: Per Protocol Population Missing FLU-PRO Plus Questionnaire Responses: Full Analysis Population 14.2.1.25 14.2.1.26 Missing FLU-PRO Plus Questionnaire Responses: Per Protocol Population

SECONDARY EFFICACY ENDPOINTS

- 14.2.2.1 Time to Resolution of COVID-19 Symptoms Based on FLU-PRO Plus COVID-19 Five Symptom Aggregate Score Using Alternate Method for Identifying Resolution: Full Analysis Population
- 14.2.2.2 Time to Resolution of COVID-19 Symptoms Based on FLU-PRO Plus COVID-19 Five Symptom Aggregate Score Using Alternate Method for Identifying Resolution: Per Protocol Population
- 14.2.2.3 Summary of Secondary Efficacy Endpoints Related to Resolution of FLU-PRO Plus Symptoms on or Before Day 10: Full Analysis Population
- 14.2.2.4 Summary of Secondary Efficacy Endpoints Related to Resolution of FLU-PRO Plus Symptoms on or Before Day 10: Per Protocol Population

14.2.2.5 Summary of Other Secondary Efficacy Endpoints: Full Analysis Population 14.2.2.6 Summary of Other Secondary Efficacy Endpoints: Per Protocol Population Supplemental Analysis of Time to Resolution of Individual FLU PRO Plus 14.2.2.7 Symptoms: Full Analysis Population Supplemental Analysis of Time to Resolution of Individual FLU PRO Plus 14.2.2.8 Symptoms: Per Protocol Population 14.2.2.9 Severity of COVID-19 Illness as Evidenced by Quality of Life Measures Using the FLU-PRO Plus Questionnaire at Each Visit: Full Analysis Population Severity of COVID-19 Illness as Evidenced by Quality of Life Measures Using 14 2 2 10 the FLU-PRO Plus Questionnaire at Each Visit: Per Protocol Population Duration of COVID-19 Illness as Evidenced by Quality of Life Measures Using 14.2.2.11 the FLU-PRO Plus Questionnaire: Full Analysis Population: Full Analysis Population 14.2.2.12 Duration of COVID-19 Illness as Evidenced by Quality of Life Measures Using the FLU-PRO Plus Questionnaire: Per Protocol Population 14.2.2.13 Clinical Course of COVID-19 as a Function of Serum 25D Concentration 50 ng/mL by Visit: Full Analysis Population Clinical Course of COVID-19 as a Function of Serum 25D Concentration 30 14.2.2.13.1 ng/mL by Visit: Full Analysis Se Clinical Course of COVID-19 as a Function of Serum 25D Concentration 100 14.2.2.13.2 ng/mL by Visit: Full Analysis Population 14.2.2.14 Clinical Course of COVID-19 as a Function of Serum 25D Concentration 50 ng/mL by Visit: Per Protocol Population 14.2.2.14.1 Clinical Course of COVID-19 as a Function of Serum 25D Concentration 30 ng/mL by Visit: Per Protocol Population Clinical Course of COVID-19 as a Function of Serum 25D Concentration 100 14.2.2.14.2 ng/mL by Visit: Per Protocol Population

SAFETY OUTPUTS

14.3.1.1	Overall Summary of Subjects with Treatment-Emergent Adverse Events: Safety Population
14.3.1.2	Incidence of Treatment-Emergent Adverse Events by SOC and Preferred Term: Safety Population
14.3.1.3	Incidence of Serious Treatment-Emergent Adverse Events by SOC and Preferred Term: Safety Population
14.3.1.4	Incidence of Treatment-Emergent Adverse Events Leading to Discontinuation of Study by System Organ Class and Preferred Term: Safety Population
14.3.1.5	Incidence of Treatment-Emergent Adverse Events Leading to Discontinuation of Treatment by System Organ Class and Preferred Term: Safety Population
14.3.1.6	Incidence of Treatment-Emergent Adverse Events Definitely Related to Study Drug by SOC and Preferred Term: Safety Population
14.3.1.7	Incidence of Treatment-Emergent Adverse Events Probably Related to Study Drug by SOC and Preferred Term: Safety Population
14.3.1.8	Incidence of Treatment-Emergent Adverse Events Possibly Related to Study Drug by SOC and Preferred Term: Safety Population
14.3.1.9	Incidence of Treatment-Emergent Adverse Events Unrelated to Study Drug by SOC and Preferred Term: Safety Population
14.3.1.10	Incidence of Mild Treatment-Emergent Adverse Events by SOC and Preferred Term: Safety Population
14.3.1.11	Incidence of Moderate Treatment-Emergent Adverse Events by SOC and Preferred Term: Safety Population
14.3.1.12	Incidence of Severe Treatment-Emergent Adverse Events by SOC and Preferred Term: Safety Population
14.4.1	Subjects with Physical Examination Shift from Normal at Screening to Clinically Significant at End of Trial: Safety Population
14.4.2	Vital Sign Results and Change from Baseline to Each Visit: Safety Population
14.4.3.1	ECG Interpretation and Shifts from Screening to Each Visit: Safety Population
14.4.3.2	ECG Results at Each Visit and Change from Baseline: Safety Population
14.4.4.1	Hematology Results at Each Visit and Change from Baseline: Safety Population
14.4.4.2	Serum Chemistry Results at Each Visit and Change from Baseline: Safety Population
14.4.4.3	Incidence of Hypercalcemia and Hyperphosphatemia Overall and at Each Visit: Safety Population

TREATMENT COMPLIANCE

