Data from Studies CTAP101-CL-1011, CTAP101-CL-1020 and 170074 show that an oral loading dose of 900 mcg of Rayaldee (CTAP101 Capsules) in the fasting state (approximately 25% BA) will raise serum 25D levels within ~9-12 hours by about 20-35 ng/mL, depending on the subject's body weight (the higher the body weight, the lower the expected increase in 25D). Many COVID-19 subjects are expected to have higher than normal body mass index (BMI) values in view of the latest reported US data. Each maintenance dose of Rayaldee (CTAP101 Capsules) (60 mcg/day) will increase serum 25D by another 0.6 ng/mL, as shown in Studies CTAP101-CL-3001, CTAP101-CL-3002 and CTAP101-CL-3003 [Sprague et al, 2016]. It follows that subjects having a baseline 25D level of ~25 ng/mL will reach ~45-60 ng/mL after the loading dose and ~59-74 ng/mL after 24 days of maintenance dosing. Subjects with slightly lower baseline levels of 25D will reach proportionately lower levels on treatment. There will be some subjects who have a higher baseline 25D level. For this reason, 25D levels will be checked at Days 7, 14 and 21 and dosing will be adjusted if levels exceed 100 ng/mL. FDA has approved Rayaldee (CTAP101 Capsules) to raise levels up to a target of 100 ng/mL in kidney patients (see APPENDIX 2.: Package Insert).

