12.3 Pharmacokinetics

Absorption

No food effect study was conducted with 30 mcg and 60 mcg doses of RAYALDEE. However, a food effect study with a supratherapeutic dose of 450 mcg in healthy subjects showed an approximately 5-fold increase in maximum serum calcifediol concentration (C_{max}) and a 3.5-fold increase in AUC_{0-t} when RAYALDEE was administered with a high fat, high calorie meal compared to fasting.

Exposure to calcifediol increased proportionally over the dose range of 30 to 90 mcg following repeated daily administration of RAYALDEE at bedtime to subjects with secondary hyperparathyroidism, chronic kidney disease and vitamin D insufficiency. Steady-state levels of serum total 25-hydroxyvitamin D are reached after approximately 3 months [see Clinical Studies (14)].

Distribution

Calcifediol is extensively bound to plasma proteins (>98%). The mean apparent volume of distribution is 8.8 L in healthy subjects following a single oral dose of RAYALDEE, and 30.1 L in subjects with stage 3 or 4 chronic kidney disease following repeated dosing.

Elimination

The mean elimination half-life of calcifediol is approximately 11 days in healthy individuals following a single dose of RAYALDEE, and approximately 25 days in patients with stage 3 or stage 4 chronic kidney disease following repeated once daily dosing.

Metabolism

Production of calcitriol from calcifediol is catalyzed by the 1-alpha-hydroxylase enzyme, CYP27B1, located in the kidney and other tissues. CYP24A1, located in all vitamin D-responsive tissues, catabolizes both calcifediol and calcitriol to inactive metabolites.

Excretion

Excretion of calcifediol occurs primarily through the biliary fecal route.

Specific Populations

Age, Gender and Race

Based on a population pharmacokinetic analysis, age, gender and race had no meaningful impact on steady-state concentrations of calcifediol following RAYALDEE administration.

Hepatic Impairment

The pharmacokinetics of RAYALDEE have not been investigated in patients with hepatic impairment.

Renal Impairment

Based on the population pharmacokinetics analysis, there was no meaningful difference in calcifediol steady-state concentrations following repeated RAYALDEE administration in patients with stage 3 or stage 4 chronic kidney disease.

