4.4 Per-Protocol Population

The per-protocol (PP) set, defined as subjects who do not have a major protocol deviation prior to resolution of the aggregated five symptoms, will also be used as supportive evidence of efficacy. Subjects who are non-compliant with the requirements of the protocol after achieving resolution of the five COVID-19 symptoms will be included in the PP set due to the expectation that such subjects will likely discontinue prematurely from the study.

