4.5 Protocol Deviations

Protocol deviations are any intentional or unintentional changes from an Investigational Review Board (IRB) approved protocol that are not approved by the IRB prior to initiation of the change. All known protocol deviations are collected by electronic data capture (EDC). Major protocol deviations are deviations that result in increased risk to subjects, affect the rights, safety, or welfare of the subjects or affect the integrity of the study. Major protocol deviations may include, but are not limited to, deviations from the inclusion/exclusion criteria, informed consent deviations, concomitant medication restrictions, and any other protocol requirement that results in a significant, added risk to the subject or has an impact on the quality of the data collected or the outcome of the study. Detailed definitions of major protocol deviations are delineated in the "CTAP101-CL-2014 Study Protocol Deviation Plan." Upon completion of the study, any subject with a major protocol deviation prior to resolution of the aggregated five symptoms will be excluded from the PP population. All protocol deviations will be presented in by-subject listings, and subjects excluded from the PP population will be documented before database lock.

ENDPOINTS 5

5.1 **Primary Safety Endpoints**

The safety and tolerability of Rayaldee (CTAP101 Capsules) will be evaluated using the following assessments:

- Adverse Events;
- Physical Examinations;
- Vital Signs;
- Electrocardiograms; and,
- Hematology and Clinical Chemistries.

Special attention will be given to changes in serum total calcium (corrected for serum albumin), serum phosphorus, and estimated glomerular filtration rate (eGFR).

5.2 **Primary Efficacy Endpoints**

The primary efficacy endpoints are:

- 1. Attainment of serum total 25D levels ≥50 ng/mL, as assessed at Day 14.

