6.10 Efficacy Analyses

6.10.1 Primary Efficacy Endpoints

The two primary efficacy endpoints will be tested hierarchically to maintain an overall one-sided alpha level of 0.025. Therefore, the test of resolution of symptoms based on the aggregate FLU-PRO Plus[©] symptom score will be performed only if the attainment of serum 25D levels \geq 50 ng/mL at Day 14 is significant at <0.025.

The first primary efficacy endpoint, attainment of serum 25D levels at ≥50 ng/mL, will be assessed with a Chi-square statistic at Day 14. The serum 25D levels will also be compared between treatment groups at Days 7, 21 and 28 with a Chi-square statistic.

The second primary efficacy endpoint is the number of days to resolution of symptoms, defined as a reduction in the aggregate FLU-PRO Plus[©] score for the selected five COVID-19 symptoms recorded on Day 0 (prior to study drug initiation) to or below 5 for a minimum of three consecutive days. The time to resolution is defined as the number of days from Day 1 (study drug initiation) to the first day of achieving the aggregate ≤5 score for a minimum of three consecutive days, provided that no score greater than 5 is recorded between the two qualifying scores. Resolution will be determined by the first two successive qualifying scores which span a minimum of three consecutive days. For clarity, resolution will be considered as having been achieved if two successive aggregate scores of ≤5 are recorded on the first day of this occurrence and on a subsequent day that is at least two days (but not more than 5 days) later even if no score has been recorded between the two days. Missing symptom score values will be handled as described in Section 6.2. The number of days to resolution will be analyzed with a Cox proportional hazards model with covariates (baseline aggregate FLU-PRO Plus[©] score for the selected five COVID-19 symptoms, baseline serum 25D, and body weight).

As a sensitivity analysis of the resolution of symptoms, a tipping point approach will be used starting with the analysis in which scores are available for three consecutive days, with no missing interval, followed by increasing numbers of missing days in the up to five-day interval, that is, 1, 2 and 3 missing days between the two consecutive qualifying scores.

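### The per-protocol set is cut off at symptom resolution but reused for 25D attainment by visit, so subjects off drug or on added vitamin D can sit in the per-protocol 25D tables

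*SAP*

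**What the plan says.** SAP 4.4 describes the PP set as "defined as subjects who do not have a major protocol deviation prior to resolution of the aggregated five symptoms" and adds: "Subjects who are non-compliant with the requirements of the protocol after achieving resolution of the five COVID-19 symptoms will be included in the PP set". The reason it gives is that such subjects are expected to leave the study early. SAP 4.5 restates the exclusion: "any subject with a major protocol deviation prior to resolution of the aggregated five symptoms will be excluded from the PP population". Protocol 9.5 has the same definition. No other PP set is defined, and the set's role is that it "will also be used as supportive evidence of efficacy".

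SAP 8.1 applies this set to serum 25D in table 14.2.1.2, "Attainment of Serum 25D Levels >=50 ng/mL by Visit: Per Protocol Population", and by subgroup in table 14.2.1.4. Under SAP 6.10.1 the primary 25D test is at Day 14, and 25D is also compared "between treatment groups at Days 7, 21 and 28 with a Chi-square statistic".

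Three other provisions bear on the point:
- Protocol 6.9 keeps subjects who are withdrawn from treatment in the study, with all assessments, unless they withdraw consent.
- Protocol 5.4 restricts vitamin D therapy and supplements during the study.
- SAP 6.2 sets a missing Day 14 25D result to failure only when it is due to intercurrent illness, hospitalization or death. Where responder status is otherwise not determinable, it is multiply imputed.

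**The concern.** For time to resolution, the cut-off is sensible: a deviation after the event cannot change the event. For a serum level drawn on a fixed day it is not, because the doses taken between resolution and the sample help determine the result. A subject who resolves on Day 4, takes no maintenance dose and still attends visits remains in the PP 25D table at Days 14, 21 and 28. So does a subject who starts vitamin D supplements after resolving.

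A reader will take the PP 25D table as showing what the regimen achieves when taken as planned. As defined, it mixes in subjects who did not take it that way. Stopping in the active arm would lower attainment; added vitamin D in the placebo arm would raise it. Both shrink the contrast. Supplements in the active arm would act in the opposite direction. Close agreement between the PP and full-analysis tables could then be read as robustness when it partly reflects the shared off-drug subjects. The relaxation also depends on a post-randomisation outcome: if the drug works, it starts earlier in the active arm.

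**Working it through.** **Inputs.** Protocol 3.2: baseline 25D averaging about 20-25 ng/mL; a loading rise "by about 20-35 ng/mL, depending on the subject's body weight"; 0.6 ng/mL per maintenance dose. Protocol Appendix 2, section 12.3: "The mean elimination half-life of calcifediol is approximately 11 days in healthy individuals following a single dose of RAYALDEE", and about 25 days in stage 3-4 chronic kidney disease. SAP 3.3: 25% versus 75% attainment by Day 28, 19 per group needed, 80 planned; 50% versus 70% resolution by Day 28.

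**Plan's own figures.**
- Level on drug = baseline + loading rise + 0.6 x maintenance doses. At baseline 25 after 24 doses: 25 + 20 + 14.4 = 59.4 to 25 + 35 + 14.4 = 74.4, which matches Protocol 3.2 (59-74).
- Pooled two-proportion formula, 25% versus 75%: (1.960 x 0.7071 + 1.2816 x 0.6124)^2 / 0.25 = 18.8, so 19 per group, as stated; power at 19 is 0.902.
- Hazard ratio: ln(0.3)/ln(0.5) = 1.74, as stated.

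**How many subjects the carve-out can reach.** With a constant hazard (assumption), the share resolved by Day 14 is 1 - 0.3^0.5 = 45% (active) and 1 - 0.5^0.5 = 29% (control). From resolution onward, no deviation excludes them. These are ceilings; the documents do not say how many of them stop the drug.

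**Level after stopping.** With last dose on day s, visit on day v and half-life h, assuming that the increment decays toward baseline:

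level = baseline + [rise + 0.6 x (s - 3)] x 2^(-(v - s)/h)

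Stop after Day 3, visit Day 14:
- h = 11: 20 + 20 x 0.5 = 30.0 to 25 + 35 x 0.5 = 42.5 ng/mL.
- h = 25: 20 + 20 x 0.737 = 34.7 to 25 + 35 x 0.737 = 50.8 ng/mL.

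Later stops, baseline 25, rise 20-35 (ng/mL):

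| Last dose | Visit | h = 11 d | h = 25 d |
|---|---|---|---|
| Day 7 | Day 14 | 39.4-49.1 | 43.4-55.8 |
| Day 10 | Day 14 | 43.8-55.5 | 46.7-60.1 |
| Day 7 | Day 28 | 31.0-35.0 | 37.5-45.9 |
| Day 10 | Day 28 | 32.8-37.6 | 39.7-48.8 |
| Day 13 | Day 28 | 35.1-40.9 | 42.2-52.0 |

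On drug at baseline 25, the projection is 51-66 on Day 14 (10 maintenance doses) and 59-74 on Day 28. The on-drug figures follow the plan in adding rises without decay, so the gap between on-drug and off-drug levels may be overstated.

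**Dilution, illustration only.** Let a share f of the active PP arm be off drug, with 75% attainment in the rest. If every one of them is below 50, attainment is 0.75 x (1 - f): 67.5%, 60% and 45% for f = 10%, 20% and 40%. Against 25% in control, with 80 per group, power is above 99.9%, 99.7% and 76.0%. If half of them still reach 50, then at f = 50% attainment is 62.5% and power 99.9%. The shares f are assumptions, the 75% is a Day 28 planning figure, and 80 per group treats the PP set as complete.

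**The case against.** A reader might infer that subjects who resolve early and stop are counted as per-protocol 25D failures. The documents do not say so. A subject with a sample is classed by the measured level. A missing result is set to failure only for the three reasons in SAP 6.2; otherwise it goes to multiple imputation, with dosing compliance and other 25D values as covariates. SAP 4.4 expects these subjects to leave the study, and for those who do, later samples are mostly imputed and not measured low. The projections apply only to those who stop and still give samples.

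Nor is failure certain at Day 14, the only primary 25D time point: stopping on Day 7 to 10 can leave a subject on either side of 50. Protocol 3.2 expects some higher baselines. Conversely, a fully compliant subject with baseline 20 and rise 20 is projected at 20 + 20 + 6 = 46, below 50 without having stopped.

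The plan also gives part of the missing view. SAP 6.10.1 pre-specifies subgroups by dosing compliance (below 80% or not) and treatment duration (10 days or less, or more), and tables 14.2.1.3 and 14.2.1.4 show 25D by subgroup. The PP analysis is supportive, and dilution from stopping in the active arm is conservative. Major deviations are detailed in a separate Deviation Plan that is not provided; if stopping is not a major deviation there, some off-drug subjects would stay in any set built on major deviations alone.

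All of this stands as a limit on the consequence. It does not remove the mismatch: whatever the Deviation Plan calls major, SAP 4.4 and 4.5 let it exclude only before resolution. The subgroups address neither supplement use nor compliance up to a given visit.

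**Conclusion.** The concern holds as a mismatch between population and endpoint. The PP set is built for symptom resolution, yet it labels tables of 25D attainment at Days 7 to 28, where it can include subjects who are off drug or have added vitamin D.

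On the plan's means, and assuming decay toward baseline, a Day 3 stopper is at about 30-42.5 ng/mL on Day 14 with the 11-day half-life, or 35-51 with the 25-day one. At baseline 25, subjects who stop by Day 10 are projected below 50 by Day 28 under either half-life; one who stops on Day 13 could still reach 52 with the longer one. The dilution of the PP contrast cannot be sized from the documents, because they give no share of early stoppers.

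The consequence is limited to supportive tables. The full-analysis table 14.2.1.1 and the gate to the second primary endpoint are untouched, and the 25D endpoint has a large reserve (19 per group needed, 80 planned). It is worth correcting before unblinding because the table would otherwise not measure what its title says.

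**What to change.** In SAP 4.4, add a separate PP set for the 25D endpoint: subjects with no major protocol deviation (including vitamin D use restricted by Protocol 5.4) and with dosing compliance within the plan's own 80-120% band, both assessed up to the 25D sample of the visit analysed, regardless of symptom resolution. Because compliance is stated as its own criterion, the set does not depend on how the Deviation Plan classes stopping. Use this set for tables 14.2.1.2 and 14.2.1.4, and keep the current PP set for the symptom endpoints.

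Cost: SAP wording before unblinding, one flag per visit (Days 7, 14, 21 and 28), and a smaller set for these two supportive tables.
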